Official Title

Effects of Structured Exercise Programs on Cognitive Function, Motor Skills, and Behavioral Outcomes in Children with Attention Deficit Hyperactivity Disorder

NCT Number: Pending

Document Type: Study Protocol

Date: November 4, 2022

1. Introduction

Attention Deficit Hyperactivity Disorder (ADHD) is one of the most common neurodevelopmental disorders in childhood and is characterized by symptoms of inattention, hyperactivity, and impulsivity. In addition to behavioral symptoms, children with ADHD frequently experience impairments in executive functions, attention control, working memory, and motor coordination.

Recent research suggests that structured physical exercise programs may positively influence cognitive and motor functions in children with ADHD. Exercise-based interventions are thought to enhance neurocognitive functioning through increased arousal, improved neural efficiency, and enhanced executive control processes. Among these interventions, rhythm-based and cognitively demanding exercises have gained increasing attention.

Gince Zumba is a movement-based exercise program that combines rhythmic movements, coordination, and aerobic activity, whereas Square Stepping Exercise (SSE) involves structured step patterns requiring visuospatial processing, motor planning, and executive control. Both exercise types may provide cognitive stimulation in addition to physical activity.

The aim of this study was to investigate the effects of Gince Zumba and Square Stepping exercises on motor and cognitive functions in children with ADHD.

2. Methods

2.1 Study Design

This study was designed as a randomized controlled experimental trial with three parallel groups.

2.2 Participants

Children diagnosed with Attention Deficit Hyperactivity Disorder were recruited for the study. Participants were within the age range of **8-12** years and were diagnosed according to DSM criteria by a qualified clinician.

Inclusion criteria included:

- A clinical diagnosis of ADHD
- Being within the specified age range
- Ability to follow verbal instructions
- Ability to read and understand Turkish language
- Being under medication at least 2 months prior to the study

Exclusion criteria included:

- Presence of neurological, orthopedic, or psychiatric disorders other than ADHD
- Participation in regular structured exercise programs during the study period
- Inability to perform any physical activity

Written informed consent was obtained from parents or legal guardians prior to participation.

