2.4 Intervention Programs

Gince Zumba Group (GZG):

Participants in the Gince Zumba group participated in a structured exercise program for **8 weeks**, with **2 sessions per week**, each session lasting approximately **50 minutes**. The program included rhythmic movements, coordination tasks, and aerobic components appropriate for children.

Square Stepping Exercise Group (SSEG):

Participants in the Square Stepping Exercise group followed an **8-week SSE** program with **2 sessions per week**, each lasting **50 minutes**. The exercises involved progressively complex stepping patterns designed to challenge motor coordination and cognitive processing.

Control Group:

Participants in the control group did not participate in any regular physical activity program during the study period and continued their usual daily activities.

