2.6 Procedure

Baseline assessments were conducted prior to randomization. Following baseline measurements, participants were randomly assigned to one of the three groups. Exercise

interventions were conducted over an 8-week period. Post-intervention assessments were performed using the same measurement tools as at baseline.

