2.8 Statistical Analysis

A per-protocol analysis approach was used, and pre-test and post-test measurements were analyzed for all three groups. Statistical analyses were performed using SPSS software (IBM Corporation, Version 22, Armonk, NY, USA). One-way analysis of variance (ANOVA) and Pearson's chi-square test were used to analyze baseline demographic characteristics of the participants. To examine the primary outcome variables, a two-factor repeated measures analysis of variance (group \times time) with Bonferroni post hoc correction was applied. Within-group changes were analyzed using paired-samples t-tests. A p-value of less than 0.05 was considered statistically significant.

4. Results

Primary Outcomes

Cognitive Function

Cognitive function was assessed using the Stroop Test and the Visual-Auditory Digit Span Test. Changes from baseline to post-intervention scores were used to evaluate attention, executive functions, working memory, and cognitive processing speed. Both intervention groups demonstrated improvements in cognitive functions. The Gince Zumba group demonstrated greater gains in attention-related abilities, while the Square Stepping Exercise group showed more pronounced improvements in high-level cognitive functions."

Secondary Outcomes

Motor Performance

Motor performance was evaluated using the BlazePod Reaction Time Test. Changes in reaction time from baseline to post-intervention were analyzed. While both intervention groups exhibited significant improvements in motor performance relative to the control group, the enhancements were more pronounced in the Square Stepping Exercise group

Behavioral Symptoms

Behavioral outcomes were assessed using the Conners Parent Rating Scale. Changes in total and subscale scores from baseline to post-intervention were used to evaluate ADHD-related behavioral symptoms. Both intervention groups demonstrated significant reductions in ADHD-related behavioral symptoms relative to the control group and baseline measurements.

4. References

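### Per-protocol is the only analysis named for this randomised comparison, so children can be left out for behaviour after assignment; the exercise exclusion is one possible route

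*Protocol*

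**What the plan says.** Protocol section 2.8 states: "A per-protocol analysis approach was used, and pre-test and post-test measurements were analyzed for all three groups". No other analysis approach is named. The group-by-time repeated measures ANOVA is assigned there to the primary (cognitive) outcomes.

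Section 2.2, which opens with "Children diagnosed with Attention Deficit Hyperactivity Disorder were recruited for the study", lists among its exclusion criteria: "Participation in regular structured exercise programs during the study period".

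Section 2.6 fixes the order of events. Baseline comes first, then: "Following baseline measurements, participants were randomly assigned to one of the three groups". The 8 weeks of intervention follow, and then: "Post-intervention assessments were performed using the same measurement tools as at baseline".

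Section 2.4 says of the control arm: "Participants in the control group did not participate in any regular physical activity program during the study period and continued their usual daily activities".

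The Results section reports, for the secondary outcomes, "significant improvements in motor performance relative to the control group" and "Both intervention groups demonstrated significant reductions in ADHD-related behavioral symptoms relative to the control group and baseline measurements".

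**The concern.** A comparison with control in a randomised trial draws its strength from groups formed by chance. A per-protocol analysis may leave out children for what they did after assignment. If leaving out differs by arm and is related to improvement, the groups compared are no longer those that randomisation produced.

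The exercise exclusion deserves attention because the behaviour it names is of the same kind as the exposure under test. Take-up of outside exercise could plausibly differ by arm, since control children are offered no programme. If the criterion were applied after randomisation, it would select on something close to the treatment itself.

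At stake are the primary group-by-time comparison and the reported motor and behavioural advantages over control. With no analysis by assigned group named, a reader cannot see whether any of these depends on who was left out.

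**Working it through.** The protocol gives no figure to reproduce on this point: no sample size, take-up rate, number removed or standard deviation. The check is therefore mainly a reading of the sections together.

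1. **Place of the criterion.** It stands in the eligibility list of section 2.2, beside diagnosis, language and ability. That favours an enrolment screen.
2. **Time window.** The medication criterion in the same list is dated to at least 2 months before the study. The exercise criterion is instead tied to the study period. Section 2.4 uses the same time phrase for control children's conduct after allocation. By section 2.6, the 8 intervention weeks all fall after randomisation. A child already assigned could therefore meet the criterion as worded.
3. **Meaning of exercise.** Both active arms are themselves 8-week programmes with 2 sessions a week (section 2.4). Read literally, the criterion would exclude them, so it must mean exercise outside the study.
4. **Link to the analysis.** Section 2.8 does not connect the criterion to the per-protocol set. No section gives a removal rule or reports a removal. The step from steps 2 and 3 to children being left out is possible but not stated.
5. **Control arm.** The section 2.4 sentence, in a document that reports results, can mean that no control child joined a programme. It can also describe only the assigned condition, or only the children retained.

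**Illustration of size, all inputs assumed.** Let a fraction f of one arm take up outside exercise, with correlation r between take-up (latent normal) and improvement. Let a share q of those children have a post-test and be put back, at random. The shift in that arm's mean, in SD of change, is

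|r| × φ(z_f) × (1 − q) / (1 − f(1 − q)), with φ(z_f) = 0.1755 at f = 0.10 and 0.2800 at f = 0.20.

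- Nobody removed, or equal removal in all arms with the same r: the contrast shifts by 0.
- f = 0.10, |r| = 0.5, q = 0: 0.5 × 0.1755 / 0.90 = 0.097.
- f = 0.20, |r| = 0.3, q = 0: 0.3 × 0.2800 / 0.80 = 0.105.
- f = 0.20, |r| = 0.5, q = 0: 0.5 × 0.2800 / 0.80 = 0.175.
- The last case with q = 0.5: 0.5 × 0.2800 × 0.5 / (1 − 0.10) = 0.078; with q = 1: 0.

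The sign is unknown. These values show how the mechanism would act and do not estimate what happened here. They are not turned into error rates: the sample size is not stated, and section 2.8 applies a Bonferroni correction to post hoc comparisons, so a rate for one unadjusted test would not describe the stated procedure.

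**Cost of analysing as assigned, also assumed.** If a fraction f of control children gained the full programme effect from outside exercise, a contrast d becomes d(1 − f). For d = 0.5 SD this is 0.5 × 0.90 = 0.45 or 0.5 × 0.80 = 0.40, a loss of 0.05 to 0.10 SD.

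**The case against.** The strongest reply is that the criterion is an ordinary enrolment screen. Eligibility lists often bar concurrent programmes in such words, and nothing ties this one to the per-protocol set. What takes a child out of that set is commonly defined in a statistical analysis plan, which may exist and is not shown. This largely stands: the enrolment reading is the more natural one, and the undefined set is not itself a fault of the protocol.

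A second reply is that section 2.4 may already say that no control child joined a programme, which would make removal from that arm on this ground nil. This stands as one plain reading, though not the only one.

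A reader might go further and infer that randomised children were removed for exercising, or that the reported advantages over control come from such removal. The protocol supports neither. It reports no removal on this ground, and the bias may be zero.

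What survives is the choice made in section 2.8. Per-protocol is stated there as the approach used, so questioning it does not depend on what a separate plan might add about the definition of the set.

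**Conclusion.** The point holds as a weakness in the stated analysis approach, with the exercise criterion as one possible route and not as a separate error. Per-protocol is the only approach named for a randomised comparison, and no analysis by assigned group is named to check it.

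The size and direction of any bias cannot be computed from the protocol. Under assumed take-up of 10% or 20% in one arm only, and a correlation of 0.5 in either direction, the contrast would move by about 0.10 or 0.175 SD of change. With no removal it would not move at all. Whether any child was left out on this ground is unknown. If the sole use of per-protocol is also raised elsewhere, the two are one point and should be counted once.

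**What to change.** **Main change.** Make the primary group-by-time analysis, and the secondary comparisons with control, include every randomised child with assessments, in the assigned group, regardless of outside exercise begun after randomisation. Show the per-protocol analysis beside it as a sensitivity analysis.

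**Supporting clarification.** State how the exercise criterion was applied: at enrolment only, or also afterwards. Report by arm how many randomised children were left out on this ground, separating those with and without a post-test, or state that none were. The criterion itself should not be reworded now. The document already reports results, and new wording could describe a rule that was not the one applied.

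**Cost.** For children with both assessments this is a re-run on data already collected, and restoring children left out on this ground changes nothing if there were none. Two downsides remain. Outside exercise may dilute the contrast slightly. Children without a post-test cannot be recovered by a re-run, so the change repairs only the part of the problem for which assessments exist; the protocol does not say how large that part is.

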2.3 Randomization and Groups

Participants were randomly assigned to one of three groups:

- 1. Gince Zumba Group (GZG)**
- 2. Square Stepping Exercise Group (SSEG)**
- 3. Control Group**

2.4 Intervention Programs

Gince Zumba Group (GZG):

Participants in the Gince Zumba group participated in a structured exercise program for **8 weeks**, with **2 sessions per week**, each session lasting approximately **50 minutes**. The program included rhythmic movements, coordination tasks, and aerobic components appropriate for children.

Square Stepping Exercise Group (SSEG):

Participants in the Square Stepping Exercise group followed an **8-week SSE** program with **2 sessions per week**, each lasting **50 minutes**. The exercises involved progressively complex stepping patterns designed to challenge motor coordination and cognitive processing.

Control Group:

Participants in the control group did not participate in any regular physical activity program during the study period and continued their usual daily activities.

2.5 Outcome Measures

Assessments were conducted at baseline and after the 8-week intervention period.

Primary outcome measures included:

- Cognitive functions assessed using standardized neuropsychological tests (e.g., Stroop Test, Visual-Auditory Digit Span Test)

Secondary outcome measures included:

- Motor performance assessments (Blaze Pod Reaction Time Test)
- Behavioral symptoms evaluated using parent-reported questionnaires (Conners Parent Rating Scale)

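### The primary outcome names no score and no success rule, and the stated Bonferroni correction, on its ordinary reading, does not span the two cognitive tests

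*Protocol*

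**What the plan says.** Protocol section 2.5 opens its primary list with "Primary outcome measures included" and gives one entry: "Cognitive functions assessed using standardized neuropsychological tests (e.g., Stroop Test, Visual-Auditory Digit Span Test". No score, subtest, composite or ranking follows.

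Section 2.8 sets the analysis: "To examine the primary outcome variables, a two-factor repeated measures analysis of variance" (group × time), "with Bonferroni post hoc correction was applied". The threshold is "A p-value of less than 0.05 was considered statistically significant". The family that the Bonferroni correction covers is not stated.

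The Results text on cognitive function says "Cognitive function was assessed using the Stroop Test and the Visual-Auditory Digit Span Test", without the *e.g.*, and adds: "Changes from baseline to post-intervention scores were used to evaluate attention, executive functions, working memory, and cognitive processing speed". It then reports that the Gince Zumba group "demonstrated greater gains in attention-related abilities, while the Square Stepping Exercise group showed more pronounced improvements in high-level cognitive functions". No score is attached to either half of that contrast.

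**The concern.** The section 2.5 entry is a domain with examples, so it does not fix which number decides the trial. The Results text identifies the two tests but draws four constructs from them and names no score for any. A reader therefore cannot tell which result answers the primary question, or which score supports the reported split between attention and high-level functions.

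The analysis section does not settle the matter. It refers to several primary variables, gives one threshold of 0.05, and attaches its only correction to the ANOVA as a post hoc step. In ordinary use that step adjusts the three pairwise group comparisons for one score. It does nothing across scores. Nothing says whether the primary claim needs one test or both. Followed as written, the plan lets a significant result on either test carry the primary claim, and the false-positive risk of that claim then exceeds 5%.

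**Working it through.** The protocol gives no sample size, power or familywise error rate, so there is no figure of its own to reproduce beyond alpha = 0.05.

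**Inputs from the protocol:** three groups (section 2.3), hence three pairwise contrasts per score; two occasions (section 2.5); alpha 0.05 (section 2.8); two named tests (section 2.5 and Results).

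**Assumptions:** one score per test (k = 2); correlation between change scores of 0, 0.5 or 0.8; 10, 20 or 40 children per arm. With two occasions, the group × time F test equals a one-way ANOVA on change scores, and this is what was simulated.

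**Step 1. Either-test rule, no true effect.** For independent scores: 1 − (1 − 0.05)² = 1 − 0.9025 = 0.0975. Simulated (100,000 replicates):

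| Correlation | 10 per arm | 20 per arm | 40 per arm |
|---|---|---|---|
| 0 | 0.0976 | 0.0984 | 0.0969 |
| 0.5 | 0.0930 | 0.0926 | 0.0920 |
| 0.8 | 0.0790 | 0.0792 | 0.0794 |

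Arm size hardly matters. More scores raise the figure: for independent scores, 1 − 0.95⁴ = 0.1855 with four and 1 − 0.95⁸ = 0.3366 with eight. The protocol does not give the number of scores.

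**Step 2. Both-tests rule.** Simulated error is 0.002 to 0.021 with no effect on either score, and at most 0.05 if one score has a true effect. There is no inflation.

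**Step 3. What a within-ANOVA Bonferroni does.** It tests each of three contrasts at 0.05/3 = 0.0167 and holds about 5% for one score. The figures in step 1 concern the group × time tests, so they are unchanged.

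**Step 4. Error after an equal split.** With k = 2 each group × time test is judged at 0.05/2 = 0.025. For independent scores the familywise error is 1 − 0.975² = 0.0494; simulation over correlations 0 to 0.8 gives 0.040 to 0.050.

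Contrasts at 0.025/3 = 0.0083, made only after that score's test rejects, do not push the total above 5%:

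- If a score has no effect, any false claim on it needs its group × time test to reject, which has probability 0.025.
- If a score has an effect, at most one of its three contrasts can be truly null, which has probability at most 0.0083.
- Each score therefore contributes at most 0.025, and two contribute at most 0.05.

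**Step 5. Why no alpha should pass between scores.** Suppose score 1 has a large effect, equal in both exercise arms, and score 2 has none. Under a Holm step-down, score 2 is tested at 0.05 while score 1's null contrast is tested at 0.0083. For independent scores the error is 1 − 0.95 × 0.9917 = 0.058; simulation gives 5.3–5.9% over correlations 0 to 0.8. The plain split gives 1 − 0.975 × 0.9917 = 0.033.

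**Step 6. Power cost.** From the noncentral F, a group × time test set to 80% power at 0.05 has 0.700, 0.707 and 0.710 at 0.025 for 10, 20 and 40 per arm. If both exercise arms differ equally from control, one exercise–control contrast falls from about 0.62 at 0.0167 to 0.51–0.52 at 0.0083.

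**The case against.** **A statistical analysis plan may hold the multiplicity rule.** This is fair, and the absence of such a rule would not be a finding on its own. But defining the primary outcome is the protocol's task, and section 2.5 does it with a domain and examples. Section 2.8 also fixes its own model, correction and threshold and points to no further rule.

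**The list is not really open.** A reader might infer from the *e.g.* that any cognitive test could have been put forward as primary. The Results text does not support that: it names the two tests used. What stands is that the narrowing appears only in results, does not amend section 2.5, and still names no score.

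**The Bonferroni correction might span the tests.** Its family is not stated, so this cannot be excluded. A flat statement that nothing is controlled across tests would go too far. Even on the wider reading, the primary score and the success rule remain undefined.

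**The 8–10% is hypothetical.** This is correct. A reader might take it as this trial's error rate, but it needs an either-test rule, a score count and a correlation that the protocol does not give.

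**The attention/high-level split is only a short summary.** Score-level results may exist in a report not seen here. That limits the point to what this document allows a reader to check.

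**Conclusion.** The point holds in a limited form. It is certain from the text that no primary score is named, that no rule says whether one test or both decide the primary question, and that the reported split is tied to no score. It is probable, on the ordinary meaning of a post hoc Bonferroni correction, that nothing adjusts across the two tests.

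The size is conditional: about 8–10% familywise error in place of 5% under an either-test rule with one score per test and correlation 0 to 0.8, more with further scores, and no inflation if both tests are required. The documents do not show that the trial's actual error rate is inflated, because they state neither rule. The matter should be fixed; confidence is medium because its numerical size rests on these unstated choices.

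**What to change.** 1. In section 2.5, delete the *e.g.*, list every Stroop and Digit Span score analysed, and state which were fixed as primary before results were known.
2. Split alpha equally across those k primary scores: judge each group × time test at 0.05/k (0.025 for two).
3. Make the three pairwise contrasts for a score only where its group × time test rejects, at one third of that score's share (0.0083 for two scores). Pass no alpha between scores. State in section 2.8 that this is the family the Bonferroni correction covers.
4. If no score was pre-specified, report all scores as exploratory and make no confirmatory primary claim. Choosing a primary score now, with results known, would not repair the problem.
5. Label the attention/high-level split as post hoc unless a dated record shows that it was pre-specified.

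Cost: no new data. The existing p-values are judged again and some claims become exploratory. With two scores, a group × time test with 80% power at 0.05 falls to about 70–71%, and the loss is larger with more scores.
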